8. The radiologist compares his/her findings with the results of the investigational software. If there are areas detected by the software (detection map) that were not detected by the radiologist, the radiologist selects these areas (up to 3 areas).
9. The radiologist will fill a report in the eCRF to be used by researchers only, flagging the detected areas for biopsy sampling into:
 - a. Defined solely by the radiologist, with PI-RADS score + location.
 - b. Overlap between the radiologist and the investigational software, with PI-RADS score + location.
 - c. Defined solely by the investigational software, with location.

The location should be according to the areas identified by PI-RADS (Figure 6.4.3).

Table 6.4.1 gives an example on the report.

Table 6.4.1: Example of radiological report of findings, for research purposes only.

Pseudonym		POT0001		
Finding number	Human	Investigational software	Finding Location	PI-RADS score
1	x		Mid-PZpm-R	3
2	x		Apex-PZa-L	4
3	x	x	Base-PZpl-R	4
4		x	Mid-PZa-L	N/A

**Figure 6.4.3:** The prostate regions according to PI-RADS.

10. The radiologist fills out the report as usual without identifying whether a finding is identified by the investigational software or human, keeping the lesion number. The radiologist will add a sentence to his report indicating that some of these lesions may have been identified by investigational software.

11. The radiologist then opens Eigen Artemis Profuse software (Eigen Health, CL, USA) to delineate the prostate and suspicious lesions as usual. The radiologist semi-automatically delineates and adjusts the entire prostate after reviewing the automatic segmentation on the GUI screen. This is followed by delineation of the suspicious findings by the radiologist and the AI (up to 3 solely AI findings). Note that radiologists begin delineation in order (i.e., lesion 1, then 2, then 3, then 4, as indicated in the report in order).
12. The radiologist will export the delineations file to the Eigen ARTEMIS - Prostate Fusion Biopsy System (Eigen Health, CL, USA).
13. The urologist will review the radiologist's report and unless the patient has contraindications to prostate biopsy (due to comorbidity or remaining life expectancy) the patient will be registered for biopsy sampling procedure.
14. When the patient arrives for the biopsy, he is prepared as usual.

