15. Prior to biopsy, the operating room nurse will import the radiologist's segmentations into the Eigen ARTEMIS - Prostate Fusion Biopsy System (Eigen Health, CL, USA).
16. The urologist will perform an ultrasound scan for fusion with the MRI scan.
17. The urologist will then obtain biopsies according to the standard clinical procedure. This includes targeting the delineated suspicious areas at least once. In some cases, the urologist may perform a systematic biopsy in addition to the targeted biopsy. The urologist will ask the nurse to place each biopsied specimen in a plastic tube immediately after collection and to immediately label the tube with Lesion 1, 2, 3 ... etc. (corresponding to the lesion number assigned by the radiologist for the targeted biopsies) in addition to labelling the biopsy location according to PI-RADS (Figure 6.4.3).
18. The tubes are sent to pathology department for histopathological evaluation. Each lesion is evaluated separately. Some suspicious areas may have more than one biopsy taken from them. Then they are pooled and evaluated together to determine the overall Gleason score for each lesion separately.
19. The data will be collected by the researchers, once every week, where the patient pseudonym (e.g., POT0001) will be used to name folders and deidentify scans upon exporting. The subject's scan images are pseudonymized and exported to an encrypted external hard drive and then uploaded to the lab at HUNT cloud. The graphical report of the biopsy procedure might be exported from the ARTEMIS

system to an encrypted external hard drive and then uploaded to the laboratory at HUNT cloud. The radiologist's report on the patient is exported to the Digital Life lab at HUNT cloud. The patient's clinical information is collected and exported to the lab at HUNT cloud. The lesion-based histopathology assessment report is exported to the lab at HUNT cloud.

20. The data collected will finally be used for analyses according to primary and secondary objectives of the study.

Overall, the deviation from normal clinical practice is very small. Deviations mainly relate to subject enrollment, the inclusion of test software in image analysis, and the storage and export of data for research. Specifically, the deviation is in steps 3, 5, 7, 8, 9, 19, and 20.

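### Does the incomplete list of deviations from normal practice in section 6.4.1 hide the extra biopsies that the software causes?

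*Protocol*

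**What the plan says.** The closing paragraph of the step-by-step procedure in protocol section 6.4.1 makes three statements. It judges the size of the departure from routine care: "Overall, the deviation from normal clinical practice is very small". It describes its nature: "Deviations mainly relate to subject enrollment, the inclusion of test software in image analysis, and the storage and export of data for research". It then gives the list: "Specifically, the deviation is in steps 3, 5, 7, 8, 9, 19, and 20".

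The steps themselves say the following about software-only areas.

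- **Step 8 (listed).** Where the software marks areas that the radiologist did not find, "the radiologist selects these areas (up to 3 areas" being the cap.
- **Step 9 (listed).** The radiologist completes a research report in the eCRF, "flagging the detected areas for biopsy sampling into" three classes: radiologist only, both, or software only.
- **Step 11 (not listed).** The fusion file is prepared, including "delineation of the suspicious findings by the radiologist and the AI (up to 3 solely AI findings" being again the cap. The gland contour is adjusted after the software's segmentation has been viewed.
- **Step 13 (not listed).** After the urologist has read the report, and unless biopsy is contraindicated, "the patient will be registered for biopsy sampling procedure".
- **Step 17 (not listed).** Biopsies follow the standard procedure, and "This includes targeting the delineated suspicious areas at least once".

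Two further unlisted steps have a study element. Step 4 sets up the log linking names to study identifiers, and step 10 adds a sentence about investigational software to the clinical report.

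**The concern.** The word that introduces the list makes it read as complete; the qualifier in the sentence before it does not carry over. Yet the steps where a software-only area is drawn as a target and then sampled, 11 and 17, are left out and so appear as routine care. The summary speaks of enrolment, image analysis and data handling, and none of these covers taking tissue. Software-only areas are by definition areas that the radiologist did not find, and the example report in Table 6.4.1 gives such an area no PI-RADS score. Targeted cores from them arise from the study.

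What would be at stake is attribution of harm. If an investigator took the summary as the definition of what belongs to the study, a complication after sampling a software-only area might be put down to background care. Unnecessary targets are the cost side of the software's performance, so systematic misattribution would flatter its safety profile. Calling the departure very small would also be hard to defend for a patient with several software-only targets.

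**Working it through.** The protocol gives no figure for the size of the deviation, so there is none to reproduce. The check compares the list with the text of the steps.

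**1. Which steps are missing?**

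- Stated list: {3, 5, 7, 8, 9, 19, 20}, 7 of 20 steps.
- Unlisted steps whose text contains or carries out something specific to the study: 4 (identification log), 10 (sentence in the clinical report), 11 (software-only areas delineated; contour drawn after viewing the software's segmentation), 17 (every delineated area sampled, software-only ones included).
- 7 + 4 = 11 of 20 steps.
- Step 13 would make 12 of 20, but its text contains nothing specific to the study. Whether it departs from routine depends on what happens to a patient without a radiologist finding. The text does not describe that, and Figure 6.4.2, which summarises the biopsy decision, is not available here.

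**2. Is there a sign of a clerical slip?** The paragraph that follows the list assigns steps 3, 4, 5 to the regional health IT provider, 7, 8, 9 to the radiologist, and 4, 19, 20 to the sponsor's representatives. The union is {3, 4, 5, 7, 8, 9, 19, 20}. Removing the stated list leaves {4}. The two sentences therefore agree except for step 4, which looks like an oversight.

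**3. How much extra sampling is involved?** Let k be the number of software-only areas in a patient, with k = 0, 1, 2 or 3 under steps 8 and 11. Step 17 requires at least one biopsy per delineated area, so the added targeted biopsies number at least k × 1: none when k = 0, at least 3 when k = 3. In Table 6.4.1 three radiologist targets become four, an increase of 1/3 = 33%, and the software-only share is 1/4 = 25%. That table is labelled an example and is not an expected rate.

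**4. Is the extra sampling undisclosed?** No. A software-only area becomes a biopsy target by being selected in step 8 and flagged in step 9, and both are listed. Steps 11 and 17 carry out that decision. The software's segmentation is first opened in step 7, also listed.

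**5. Does anything depend on the list?**

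| Item | Where it is fixed | Uses the deviation list? |
|---|---|---|
| Which areas become targets | Steps 8, 9 and 11 | No |
| How they are sampled | Step 17 | No |
| Source of each target | Step 9, classes a to c, in the eCRF | No |
| Recording of adverse events | Section 14.5, all events, in medical records and eCRF | No |
| Reporting of adverse events | Section 14.4 and Table 14.4.1, cited but not in this extract | Not shown |

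A patient biopsied only on software findings is one whose step 9 report has class c entries and no class a or b entries. That can be derived from data already collected.

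**The case for a change.** The best case for acting is that listing steps 8 and 9 does not fully repair the summary. Those steps disclose selection and flagging on a report that only researchers see; the needle enters at step 17, which the protocol calls standard. An investigator judging relatedness works from the wording in front of them, and correcting it would cost very little.

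Part of this stands. The list is incomplete for steps 4, 10, 11 and 17, the summary does not mention added sampling, and the description of its size is unsupported for a patient at the cap of three.

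The step from there to a biased safety result does not stand. No text in the document makes the list a criterion for relatedness. The parts of section 14 on reporting are cited but not extracted, while the abbreviation list shows that the full plan distinguishes adverse device effects, serious and otherwise, from adverse events. Section 14.5 has every event recorded, so capture is not in doubt. Nor is concealment shown: the cap is stated in steps 8 and 11, the consent is described as explaining risks and benefits, and the extract has no risk section from which to say which risk is the main one. Separate safety tables for patients with software-only targets would be reasonable, but they commonly belong in a statistical analysis plan, which is not at hand.

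**Conclusion.** The list after step 20 is incomplete by four steps (4, 10, 11, 17), with step 13 undetermined, and the summary sentence leaves out 0 to 3 extra targeted areas per patient. Both are faults of description. Completing the list would leave every target, sampling rule, recorded item and conclusion as it is. A target-level flag for software-only findings already exists in step 9, and the patient-level version follows from it. Nothing in the plan needs to change; the paragraph can be brought into line with the steps if it is edited for another reason.

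This rests on two assumptions: that the sections on adverse-event classification and reporting, which are not in the extract, do not use the deviation list as a test of relatedness, and that the step 9 classification is completed for every target as written. If the first were false, the incomplete list would bear on how harms are attributed, and the point would need to be reopened.
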